#### 3.2 Primary Endpoint/Analysis

The study will be analyzed per the standards of the 1994 Tentative Final Monograph (TFM) for Effectiveness Testing of a Patient Preoperative Skin Preparation (FR 59:116, 17 June 94, pp. 31450-31452), as updated by recent recommendations by the FDA on responder rates. The primary efficacy criteria will be assessed based on  $\log_{10}$  CFU/cm^2 reductions at the 10-minute sampling time. The TFM indicates  $\log_{10}$  CFU/cm^2 reductions as the primary efficacy measure while the Proposed Amendment of the Tentative Final Monograph (FR 80:84, 01 May 2015) indicates responder rates as the primary efficacy requirement. This study will use responder rate at 10 minutes post-prep as the primary measure of efficacy but will also calculate and show  $\log_{10}$  CFU/cm^2 reductions from baseline.

The primary measure of antimicrobial efficacy is the reduction of skin flora on the abdominal and groin sites at 10 minutes following application of the study treatments relative to the Treatment Day baseline counts.

The reduction will be calculated by a percent successes approach (i.e. percent of subjects meeting required reductions = responder rate). A site is considered a responder for the treatment at the indicated time point if the criteria in the following table are met:

Table 3.2: Minimum and Maximum Treatment Day Baseline and Expected Mean Log10 Reduction per Anatomical Site		
Anatomical Site	Minimum and Maximum Treatment Day Baseline*	Expected Mean Log10 Reduction
Abdomen	$1.0 \times 10^3 - 3.2 \times 10^5 \text{ CFU/cm}^2$ (3.0 Log 10 – 5.5 Log 10 )	2.0 log 10 @ 10-minutes
Groin	$1.0 \times 10^5 - 3.2 \times 10^7 \text{ CFU/cm}^2$ (5.0 Log 10 – 7.5 Log 10 )	3.0 log 10 @ 10 minutes

\*Note: For the Screening Day baseline, the maximum upper limit does not apply. Only the minimum criteria must be met.

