## 6. Assessment of Efficacy

### 6.1 Efficacy Parameters

The primary measure of antimicrobial efficacy is the reduction of skin flora on the abdominal and groin sites 10 minutes following application of the study treatments relative to the Treatment Day baseline counts.

The reduction will first be calculated as  $\log_{10}$  CFU/cm^2 changes from baseline, then the percentage of successes will be calculated from the  $\log_{10}$  CFU/cm^2 reductions (i.e. percent of subjects meeting required reductions = responder rate). A site is considered a responder for the treatment at 10 minutes if it achieves  $\geq 2.0 \log_{10}$  CFU/cm^2 reduction on the abdomen or  $\geq 3.0 \log_{10}$  CFU/cm^2 reduction on the groin.

Responder status will be calculated separately for the abdomen and groin, for each test substance, for each post-treatment sample time, and for each subject. The individual responses will then be grouped to generate an overall responder rate for each anatomical area, for each test substance, and for each post-treatment sample time. The efficacy goal for active products is to have the lower bound of the 95% confidence interval for the responder rate to be greater than or equal to 70%.

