### 8.2 Statistical Methods

#### 8.2.1 Efficacy Analyses

CFU values will be calculated as per the Bacterial Enumeration methods above. Individual plate CFU counts that are zero will be treated as 0.5 for further calculations. Changes from baseline will be calculated separately for each subject and for each of the three non-baseline sites by taking the baseline  $\log_{10}$  CFU/cm^2 values and then subtracting the  $\log_{10}$  CFU/cm^2 values for the samples taken after the baseline. Therefore, a subject who completes all treatments and passes all baseline requirements will have 4 (sites) \* 3 (post-application samples per site) = 12 changes from baseline reported. Responder status will be calculated for each reported  $\log_{10}$  CFU/cm^2 reduction. The sites will be considered responders based on the sample time and body area:

For the groin at 30 seconds or 10 minutes, a  $\log_{10}$  CFU/cm^2 reduction  $\geq 3.0$  is considered a responder.

For the abdomen at 30 seconds or 10 minutes, a  $\log_{10}$  CFU/cm^2 reduction  $\geq 2.0$  is considered a responder.

For either the groin or the abdomen at 6 hours, a  $\log_{10}$  CFU/cm^2 value less than baseline (i.e., a  $\log_{10}$  CFU/cm^2 reduction  $> 0$ ) is considered a responder.

Responder statuses will be grouped by body area, sample time, and test substance. Exact confidence intervals will be calculated for responder rates. The primary efficacy goal is to have the 95% confidence intervals for the responder rate at 10

minutes to be  $\geq 70\%$ . The secondary efficacy goals are to have the 30 second and 6 hour 95% confidence intervals for the responder rates to be  $\geq 70\%$ .

Differences in responder rates between treatments and their confidence intervals will be calculated using asymptotic (approximate) methods. If differences in responder rates are not reliable based on approximate methods, which happens when rates are near either 100% or 0%,  $\log_{10}$  CFU/cm^2 confidence intervals for the differences will be used for comparison instead.

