Protocol Amendment(s): 
6. This amendment is issued after the completion of testing to add additional efficacy criteria in the below sections to the study protocol [REDACTED]  [REDACTED]
 
 
The following paragraph is added to the end of Section 3.2 Primary Endpoint/Analysis and Section 6.1 Efficacy Parameters of the protocol:
 
 
Additionally, as recommended by FDA, product effectiveness will be measured using the average treatment effects (ATE). The ATE will be estimated from a linear regression of posttreatment bacterial count (<math>\log_{10}</math> scale) at 10 minutes on the additive effect of a treatment indicator and the baseline or pretreatment measurement (<math>\log_{10}</math> scale). To show effectiveness, the test product will be 1) non-inferior to ChloraPrep® with a 0.5 margin (<math>\log_{10}</math> scale, upper bound of 95% confidence interval of the difference in ATE values <math>\leq 0.5</math>) and 2) superior to the vehicle control by a margin of 1.2 (<math>\log_{10}</math> scale, lower bound of 95% confidence interval of the difference in ATE values <math>\geq 1.2</math>).
 
 
Section 3.2 Secondary Endpoints/Analysis and 6.1 Secondary Endpoints/Analysis is revised as follows (additions underlined for clarity):
 
 
Responder rates, ATE values, and differences in ATE values at 30 seconds will be calculated identically to the 10 minute responder rates and ATE values. At 6 hours a site is considered a responder if it is below baseline; otherwise, 6 hour responder rates will be calculated identically to the 10 minute responder rates. The secondary efficacy goals are to have the 95% confidence intervals for the responder rates to be greater than or equal to 70%. Log10 CFU reduction from baseline will also be calculated for all post-prep samples. The non-inferiority and superiority goals for ATE values are identical to those at 10 minutes.
				

Date Issued: 07/12/17 [REDACTED]

Laboratory Project Identification No. 865-105  
Zurex Pharma, Inc. Project No.: ZX-ZP-0073

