**Protocol Amendment(s): (continued)**

- The following paragraphs are added to end of Section 8.2.1 Efficacy Analysis of the protocol:

Average Treatment Effect (ATE) will be estimated from a linear regression of posttreatment bacterial count ( $\log_{10}$  scale) on the additive effect of a treatment indicator and the baseline or pretreatment measurement ( $\log_{10}$  scale). ATE will be calculated for the 10 minute samples separately for each product and each body area. This will generate 3 (products) \* 2 (body areas) \* 1 (post-treatment time point) = 6 ATEs, one each for each combination of product and body area at 10 minutes. The ATEs will be compared as follows:

- a. ZuraPrep™ will be compared to the ChloraPrep®. To show effectiveness, ZuraPrep™ should be non-inferior to ChloraPrep® with a 0.5 margin. Specifically, the upper bound of the 95% confidence interval of the ATE of ChloraPrep® minus the ATE of ZuraPrep™ should be less than or equal to 0.5.
- b. ZuraPrep™ will be compared to ZuraPrep™ vehicle. To show effectiveness, ZuraPrep™ should be superior to ZuraPrep™ vehicle by a 1.2 margin. Specifically, the lower bound of the 95% confidence interval of the ATE of ZuraPrep™ minus the ATE of ZuraPrep™ vehicle should be greater than or equal to 1.2.

The same ATE calculations will be performed for the 30 second time point, but the results are for informational purposes only.

[REDACTED]

[REDACTED]

Date Issued: 10/26/17 [REDACTED]	Laboratory Project Identification No. 865-105 Zurex Pharma, Inc. Project No.: ZX-ZP-0073		
STUDY TITLE: Pivotal Clinical Evaluation of the Antimicrobial Effectiveness of Topically Applied ZuraPrep™	STUDY DIRECTOR: M. [name] CCRP Signature [REDACTED] Date 10/26/17		
TEST AND CONTROL ARTICLES: ZuraPrep™ [REDACTED] ZuraPrep™ Vehicle (Without Isopropyl Alcohol) [REDACTED] ChloraPrep® [REDACTED] (Scrub Teal® Tint)	ID/LOT NO. [REDACTED]	DATE RECEIVED: [REDACTED]	DS NO. [REDACTED]
PERFORMING DEPARTMENT(S): Clinical Laboratory	STORAGE CONDITIONS: Location: [REDACTED]  Dark  Ambient Room Temperature  Desiccator  Freezer  Refrigerator  Other		

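### Amendment 6 subtracts ATEs as if they were reductions but regresses the post-treatment count, so the superiority and non-inferiority rules point the wrong way; the regression also omits subject in a paired design

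*Combined protocol and SAP*

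**What the plan says.** Amendment 6 (07/12/17) opens: "This amendment is issued after the completion of testing to add additional efficacy criteria". Its addition to 8.2.1 says the ATE "will be estimated from a linear regression of posttreatment bacterial count" on the log10 scale, with two terms on the right-hand side: a treatment indicator and the baseline count. Six 10-minute ATEs are to be produced, one for each of three products in each of two body areas. No coding, reference level or sign convention is visible, and parts of the amendment are blacked out.

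Two rules follow.

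- Item a (non-inferiority to ChloraPrep, with a limit of 0.5): "upper bound of the 95% confidence interval of the ATE of ChloraPrep® minus the ATE of ZuraPrep™ should be less".
- Item b (superiority to vehicle): "ZuraPrep™ should be superior to ZuraPrep™ vehicle by a 1.2 margin". The operative test, with 1.2 as the figure to be reached, is "lower bound of the 95% confidence interval of the ATE of ZuraPrep™ minus the ATE of ZuraPrep™ vehicle should be greater".

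The text that Amendment 6 adds to 3.2 and 6.1 uses the same regression and margins but gives no order of subtraction.

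Elsewhere efficacy means reduction. Section 3.2 states: "The primary measure of antimicrobial efficacy is the reduction of skin flora on the abdominal and groin sites at 10 minutes", and 6.1 repeats this. Section 8.2.1 fixes the direction for changes from baseline: "Changes from baseline will be calculated separately for each subject and for each of the three non-baseline sites by taking the baseline" value and subtracting the later one. Amendment 6 does not extend that convention to the ATE.

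On design, 3.1 describes paired comparisons with two products per subject, and Treatment Balance in 3.3 puts one on each side of the body. The ANOVA in 8.2.1 for log10 changes has subject as a random term. The ATE regression has none.

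**The concern.** **Sign.** The outcome is a count, for which a better product has a lower value. The subtractions in items a and b suit an effect for which a better product has a higher value. Applied to the stated outcome, item b cannot be met by a product that beats vehicle, and item a passes a product however much worse than ChloraPrep it is. The second error is the more serious because it lets a poor product through.

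**Pairing.** Most subjects contribute one ZuraPrep and one ChloraPrep reading in each body area. A regression on treatment and baseline alone treats those two readings as independent, so its standard errors do not match the design.

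These criteria apply at the primary time point and were written after testing. Such a rule should agree with its own outcome variable without the reader having to supply the sign.

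**Working it through.** The plan gives no power or sample size for the ATE rules. The 267 in 8.3 concerns the responder rate and has no bearing here.

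**1. Sign**

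For product P, let post = a + t_P + b × baseline. Then

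reduction = baseline − post = −a − t_P + (1 − b) × baseline.

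Every between-product contrast keeps its size and standard error and changes sign. The reference level cancels in the difference, so leaving it unstated does not rescue the rule. In one simulated data set, ZuraPrep minus vehicle was −2.29 (95% CI −2.56 to −2.02) on the count, which fails item b, and +2.29 (2.02 to 2.56) on the reduction, which passes.

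Pass rates over 1,000 simulated trials per scenario are below. The 10-minute reductions are assumed: ChloraPrep 3.5 and vehicle 1.5 log10, with residual SD 1.0 and within-subject correlation 0.5.

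| True state | Rule | As written, on count | Sign corrected |
|---|---|---|---|
| ZuraPrep 2.0 better than vehicle | b | 0% | 100% |
| ZuraPrep 1.5 worse than vehicle | b | 60% | 0% |
| ZuraPrep 1.5 worse than ChloraPrep | a | 100% | 0% |
| ZuraPrep 0.8 better than ChloraPrep | a | 0% | 100% |

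For the first row, SD 0.7 or correlation 0 still gives 0% as written and 99.9-100% corrected.

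**2. Layout**

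Section 1.5 gives minimums of 320, 320 and 64 readings per body area. Two readings per subject gives (320 + 320 + 64)/2 = 352 subjects, the plan's own figure. Hence:

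- ZuraPrep-ChloraPrep pairs: 352 − 64 = 288
- ZuraPrep-vehicle pairs: 320 − 288 = 32
- ChloraPrep-vehicle pairs: 320 − 288 = 32

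**3. Standard errors**

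The correlation ρ is assumed at 0.3 and 0.6, and baseline is taken as orthogonal to product. In units of SD²:

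- Plain model variance: 1/n₁ + 1/n₂
- True variance of that estimate: 1/n₁ + 1/n₂ − 2ρ × n₁₂/(n₁n₂), where n₁₂ is the number of shared subjects
- Paired model: generalised least squares (GLS) on the 288/32/32 layout

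For ChloraPrep minus ZuraPrep, the plain variance is 2/320 = 0.00625 (SE 0.0791). The deduction is 2ρ × 288/320² = 0.005625ρ, so the true SE is 0.0675 or 0.0536. For ZuraPrep minus vehicle, the plain variance is 1/320 + 1/64 = 0.01875 (SE 0.1369). The deduction is 2ρ × 32/(320 × 64) = 0.003125ρ, so the true SE is 0.1335 or 0.1299.

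| Contrast | ρ | Plain/true SE | Actual coverage | GLS SE | Plain/GLS width |
|---|---|---|---|---|---|
| ChloraPrep − ZuraPrep | 0.3 | 1.17 | 97.8% | 0.0669 | 1.18 |
| ChloraPrep − ZuraPrep | 0.6 | 1.47 | 99.6% | 0.0510 | 1.55 |
| ZuraPrep − vehicle | 0.3 | 1.03 | 95.6% | 0.1277 | 1.07 |
| ZuraPrep − vehicle | 0.6 | 1.05 | 96.1% | 0.1050 | 1.30 |

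Coverage is 2Φ(1.96 × plain/true) − 1. The ratios do not depend on SD.

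**4. Effect on the non-inferiority decision (correct sign)**

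At SD 1.0 (assumed), the half-width is 1.96 × 0.0791 = 0.155 plain, against 0.131 (ρ = 0.3) or 0.100 (ρ = 0.6) paired. If ZuraPrep is truly 0.3 log10 worse than ChloraPrep, it passes with probability Φ[(0.5 − 0.3 − half-width)/sampling SE]:

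- Plain: 75% (ρ = 0.3) and 80% (ρ = 0.6)
- GLS: 85% and about 97.5%
- Plain estimate with a subject-clustered SE (half-width 1.96 × true SE): 84% and 96%

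At a true deficit of exactly 0.5, the plain rule passes with probability Φ(−1.96 × plain/true) = 1.1% or 0.2%, against 2.5% nominal. If the two products are equal, both the plain and GLS analyses pass at least 99.6% of the time at SD 0.5-1.5.

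**The case against.** **The direction is clear from context, and the coding is not stated.** Items a and b use the words non-inferior and superior, efficacy is defined as reduction in 3.2 and 6.1, and 8.2.1 takes baseline minus post. The wording added to 3.2 and 6.1 carries no reversed sign. On this view the amendment only leaves the sign and reference level undefined, and a blacked-out passage might define them. The intent is indeed inferable, and the chance that the analysis was run backwards is small. But the reference level cancels in a between-product difference. On the outcome the amendment names, the most specific statement of each rule gives the wrong answer. The limit set by the redactions stands.

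**Pairing is conservative.** The amendment is silent on the variance estimator, and the regression is described as recommended by FDA. No false passes arise, and vehicle-contrast coverage is close to nominal. Sites failing the Treatment Day baseline are dropped, which breaks pairs: if 20% of sites failed independently (an assumption), the width ratio of 1.18-1.55 would fall to 1.15-1.46. All of this stands, and it makes pairing the lesser part.

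**Narrowing intervals after testing makes non-inferiority easier to claim.** This is a fair caution. However, the random subject term was already specified for the log10 changes, and clustered standard errors keep the recommended regression and its point estimates. Reporting the model used makes the choice visible.

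**Conclusion.** Both parts hold and should be fixed. The sign defect is the main one. On the stated outcome, the superiority rule cannot be met by a product that works, and the non-inferiority rule does not limit inferiority. This follows from algebra; the simulated pass rates only illustrate it. It rests on reading the ATE as an effect on the count, which is what the visible text describes.

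The pairing omission makes both intervals too wide when within-subject correlation is positive, and mainly affects ZuraPrep against ChloraPrep. It affects the decision only when the true difference is near the margin, where it can miss real non-inferiority. Its size depends on the assumed correlation and SD and on the planned minimum layout; the documents give no correlation or SD.

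**What to change.** 1. **Sign.** Define the ATE as the baseline-adjusted log10 reduction (baseline minus post-treatment) and keep the subtractions. Alternatively keep the count and reverse both: ZuraPrep minus ChloraPrep with upper bound ≤ 0.5, and vehicle minus ZuraPrep with lower bound ≥ 1.2. The margins do not change.
2. **Model.** Take both contrasts from one model per body area containing all three products, baseline as covariate and subject as a random effect. If the FDA-recommended regression must be kept, use subject-clustered standard errors.
3. **Reporting.** If the analysis has already been run, state the sign and model used in the final report under 8.6.
4. **Minor, separate.** Amendment 6 gives the 30-second ATE the 10-minute goals in its text for 3.2 and 6.1, but treats it as information only in its text for 8.2.1. Reconcile the two.

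Items 1 and 2 cost one sentence each, and no new data are needed.
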